6.2.2.2 Day 15 (lab visit only)

- CBC with differential and platelet count and serum chemistries (Na, K, Cl, HCO₃, BUN, Cr, Ca, Alb, TBili, AST, ALT, ALP)

6.2.3 Cycle 3 and beyond

6.2.3.1 Day 1

- Focused physical exam
- Vital signs and weight
- ECOG PS
- CBC with differential and platelet count and serum chemistries (Na, K, Cl, HCO₃, BUN, Cr, Ca, Alb, TBili, AST, ALT, ALP)
- TSH

CONFIDENTIAL

- PT/INR
- AFP (only if elevated at screening)
- Serum pregnancy test for beta HCG (for women of childbearing potential, defined in Appendix A)
- HBV DNA PCR if hepatitis B surface antigen or core antibody previously positive
- Review of concomitant medications
- Review of abemaciclib pill diary
- Dispensing of abemaciclib and return of unused pills
- AE assessment
- Nivolumab treatment
- Blood draw (50cc) for correlative research studies (procedures described in laboratory manual)
- Disease assessment (CT or MRI) with 7 days of day 1 of cycle 3, 5, and every other subsequent cycle

6.2.4 End of Study Visit (within 30 days of end of protocol therapy)

- Focused physical exam
- Vital signs and weight
- ECOG PS
- CBC with differential and platelet count and serum chemistries (Na, K, Cl, HCO₃, BUN, Cr, Ca, Alb, TBili, AST, ALT, ALP)
- TSH
- AFP (only if elevated at screening)
- Serum pregnancy test for beta HCG (for women of childbearing potential, defined in Appendix A)
- HBV DNA PCR if hepatitis B surface antigen or core antibody previously positive
- Review of concomitant medications
- Review of abemaciclib pill diary
- Return of unused abemaciclib pills
- AE assessment
- Blood draw (50cc) for correlative research studies (procedures described in laboratory manual)
- Disease assessment (CT or MRI) if not performed within prior 28 days

The end of study visit can be conducted during a scheduled office visit (such as to review scans demonstrating progression) or separately.

6.2.5 Follow-Up Phase of the Study

All subjects will be followed for survival, disease status and new anti-cancer treatment information unless the subject requests to be withdrawn from follow-up or the study is terminated by the Principal Investigator. Follow-up information will be collected via telephone or subject medical records until death, loss to follow-up, or study termination by the Principal Investigator, whichever occurs first. Subjects will be followed every 6 months up for a maximum of 24 months from the end of protocol therapy. If the subject no longer wishes to be contacted but maintains his or her consent, the study staff may use a public information source (e.g. newspaper or electronic obituary, county records) to obtain information about survival status only as per local data protection laws and approval from the relevant ethics committee.

6.2.6 Subject Withdrawal

Subjects may withdraw from the study at any time without impact to their care. They may also be discontinued from the study at the discretion of the Investigator for lack of adherence to intervention or study procedures or visit schedules or unacceptable toxicity of the therapy. The Investigator may also withdraw subjects who violate the study plan, or to protect the subject for reasons of safety or for administrative reasons. It will be documented whether or not each subject completes the clinical study. Subjects who withdraw early will have one final visit to collect investigational product and to follow up regarding adverse events.

If a subject permanently discontinues all study treatment for reasons other than disease progression, such as toxicity, the state of disease in terms of progression should be noted at this time point. Ideally formal

CONFIDENTIAL

imaging should occur at this point to document the state of disease. Alternatively, the previous scan should be used. Where possible scanning should continue as per normal practice (RECIST v1.1) until progression has been reached as per protocol or the subject has started other anti-cancer treatment. The date of progression of disease should be recorded in the eCRF. Further treatment is at the treating doctor's discretion.

6.2.7 Data Collection and Follow-Up for Withdrawn Subjects

Subjects who withdraw consent to participate in the study will be seen for one final visit to collect the investigational product. During this visit they will be asked for permission to have the study team look into their survival status via publicly available means.

7 Study Evaluations and Measurements

7.1 Informed Consent

Study personnel will obtain written informed consent from each subject **prior** to participation in this study, following adequate explanation of the aims, eligibility criteria, treatment and follow-up procedures, anticipated benefits and potential risks of the study.

7.2 Medical History and Demographic Data

A complete medical history will be obtained including details of any relevant medical conditions occurring prior to consent. Details will be collected on the subject's cancer diagnosis including site, date of diagnosis, radiological tumor size, prior anti-cancer treatment (if any) and outcome, medications and their indications, history of alcohol use, history of viral hepatitis (including prior and/or ongoing treatments and current disease status), history of non-alcoholic steatohepatitis (NASH), history of autoimmune liver disease, history of liver cirrhosis, and Child-Pugh score. Demographic data collected will include sex, date of birth and race/ethnicity.

7.3 Physical Examination

A complete physical examination will be conducted at specified visits. A focused physical assessment will be performed at other visits as determined by the Investigator or directed per subject complaints

7.4 Vital Signs, Height, and Weight

Vital signs including oxygen saturation, heart rate, respiration rate, blood pressure, and oral temperature will be measured at specified visits. Height will be collected at the baseline or screening visit. Weight will be collected at specified visits.

7.5 ECOG Performance Status

ECOG performance status will be measured at specified visits according to **Table 7**

Table 7: ECOG Performance Status

ECOG Grade	ECOG Status
0	Fully active, able to carry on all pre-disease performance without restriction
1	Restricted in physically strenuous activity but ambulatory and able to carry out work of a light or sedentary nature, e.g., light house work, office work

CONFIDENTIAL

This material is the property of the University of Pennsylvania.

2	Ambulatory and capable of all self-care but unable to carry out any work activities. Up and about more than 50% of waking hours
3	Capable of only limited self-care, confined to bed or chair more than 50% of waking hours
4	Completely disabled. Cannot carry on any self-care. Totally confined to bed or chair
5	Dead

7.6 Concomitant Medications

All medications (including prescription medications and over the counter preparations), taken by the subject from the day of consent to the safety visit will be documented as concomitant medications. All medication should be recorded to clearly allow identification of prohibited medications. If a subject is taking any of the medications defined as prohibited for use during the study, then these will be documented during screening. Subjects must stop taking any prohibited medications prior to starting study treatment within the specified wash out periods of the prohibited medications. The following details will be collected: drug name, reason for treatment, dose/units, route of administration, frequency, start and end date of therapy.

Patients must be instructed not to take any medications, including over-the-counter products such as vitamins, minerals and other dietary supplements, without first consulting the Investigator. All concomitant medications must be recorded on the relevant eCRF.

Supportive care and other medication, which is considered necessary for the patient's safety and well-being, may be given at the discretion of the investigator and recorded in the relevant eCRF.

Patients who use oral contraceptives, hormone replacement therapy, prophylactic or therapeutic anticoagulation therapy (such as low molecular weight heparin or warfarin at a stable dose level), or other allowed maintenance therapy should continue their use.

Abemaciclib is predominantly cleared by oxidative metabolism via CYP3A4. Clinical drug interaction studies with a CYP3A inhibitor and CYP3A inducer significantly altered the PK of abemaciclib and its circulating major metabolites. Therefore, drugs that are strong and moderate inducers of CYP3A and/or strong inhibitors of CYP3A should be avoided or substituted if necessary.

If concomitant use cannot be avoided, abemaciclib dose adjustments may be required:

- Patients who must take CYP3A inhibitors such as clarithromycin, diltiazem, or verapamil should reduce the abemaciclib dose to 100 mg twice daily.
- Patients who must take itraconazole should reduce the abemaciclib dose to 50 mg twice daily.
- Patients should avoid using ketoconazole
- Patients should avoid grapefruit or grapefruit juice.

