1.2.1 Clinical Data to Date

1.2.1.1 Human Pharmacokinetics

The pharmacokinetics of abemaciclib were characterized in patients with solid tumors, including metastatic breast cancer, and in healthy subjects. Following single and repeated twice daily dosing of 50 mg (0.3 times the approved recommended 150 mg dosage) to 200 mg of abemaciclib, the increase in plasma exposure (AUC) and Cmax was approximately dose proportional. Steady state was achieved within 5 days following

CONFIDENTIAL

repeated twice daily dosing, and the estimated geometric mean accumulation ratio was 2.3 (50% CV) and 3.2 (59% CV) based on Cmax and AUC, respectively.

Absorption

The absolute bioavailability of abemaciclib after a single oral dose of 200 mg is 45% (19% CV). The median Tmax of abemaciclib is 8.0 hours (range: 4.1-24.0 hours).

Effect of Food

A high-fat, high-calorie meal (approximately 800 to 1000 calories with 150 calories from protein, 250 calories from carbohydrate, and 500 to 600 calories from fat) administered to healthy subjects increased the AUC of abemaciclib plus its active metabolites by 9% and increased Cmax by 26%.

Distribution

In vitro, abemaciclib was bound to human plasma proteins, serum albumin, and alpha-1-acid glycoprotein in a concentration independent manner from 152 ng/mL to 5066 ng/mL. In a clinical study, the mean (standard deviation, SD) bound fraction was 96.3% (1.1) for abemaciclib, 93.4% (1.3) for M2, 96.8% (0.8) for M18, and 97.8% (0.6) for M20. The geometric mean systemic volume of distribution is approximately 690.3 L (49% CV). In patients with advanced cancer, including breast cancer, concentrations of abemaciclib and its active metabolites M2 and M20 in cerebrospinal fluid are comparable to unbound plasma concentrations.

Elimination

The geometric mean hepatic clearance (CL) of abemaciclib in patients was 26.0 L/h (51% CV), and the mean plasma elimination half-life for abemaciclib in patients was 18.3 hours (72% CV).

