- Ketoconazole (a strong CYP3A inhibitor) is predicted to increase the AUC of abemaciclib by up to 16-fold.
- Itraconazole (a strong CYP3A inhibitor) is predicted to increase the relative potency adjusted unbound AUC of abemaciclib plus its active metabolites (M2, M18 and M20) by 2.2-fold.
- Coadministration of 500 mg twice daily doses of clarithromycin (a strong CYP3A inhibitor) with a single 50 mg dose of abemaciclib (0.3 times the approved recommended 150 mg dosage) increased the relative potency adjusted unbound AUC 0-INF of abemaciclib plus its active metabolites (M2, M18, and M20) by 1.7-fold relative to abemaciclib alone in cancer patients.

Moderate CYP3A Inhibitors:

- Diltiazem and verapamil (moderate CYP3A inhibitors) are predicted to increase the relative potency adjusted unbound AUC of abemaciclib plus its active metabolites (M2, M18, and M20) by 1.7-fold and 1.3-fold, respectively.

Strong CYP3A Inducers:

- Coadministration of 600 mg daily doses of rifampin (a strong CYP3A inducer) with a single 200 mg dose of VERZENIO decreased the relative potency adjusted unbound AUC0-INF of abemaciclib plus its active metabolites (M2, M18, and M20) by 67% in healthy subjects.

Moderate CYP3A Inducers:

- The effect of moderate CYP3A inducers on the pharmacokinetics of abemaciclib is unknown.

Loperamide:

- Co-administration of a single 8-mg dose of loperamide with a single 400-mg dose of abemaciclib in healthy subjects increased the relative potency adjusted unbound AUC0-INF of abemaciclib plus its active metabolites (M2 and M20) by 12%, which is not considered clinically relevant.

Fulvestrant:

- In clinical studies in patients with breast cancer, fulvestrant had no clinically relevant effect on the pharmacokinetics of abemaciclib or its active metabolites.
-

Effects of Abemaciclib on Other Drugs

Loperamide:

- In a clinical drug interaction study in healthy subjects, coadministration of a single 8 mg dose of loperamide with a single 400 mg abemaciclib (2.7 times the approved recommended 150 mg dosage) increased loperamide AUC0-INF by 9% and Cmax by 35% relative to loperamide alone. These increases in loperamide exposure are not considered clinically relevant.

Metformin:

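### Section 7.6 fixes abemaciclib doses with CYP3A inhibitors but makes no provision for subjects already reduced for toxicity

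*Combined protocol and SAP*

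**What the plan says.** Section 7.6 (Concomitant Medications) asks that strong CYP3A inhibitors, and strong or moderate inducers, be avoided or substituted. It then continues: "If concomitant use cannot be avoided, abemaciclib dose adjustments may be required". Two fixed targets follow: "Patients who must take CYP3A inhibitors such as clarithromycin, diltiazem, or verapamil should reduce the abemaciclib dose to 100 mg twice daily" and "Patients who must take itraconazole should reduce the abemaciclib dose to 50 mg twice daily". Neither refers to the dose the subject is taking when the inhibitor starts. The section also tells patients not to take any medication "without first consulting the Investigator".

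Table 1 in section 3.1.1 sets the levels for toxicity reductions: 150 mg, 100 mg (level -1) and 50 mg (level -2) twice daily, with permanent discontinuation if a dose below 50 mg is needed. These reductions are triggered by toxicity at least possibly related to abemaciclib. Starting an interacting drug is not a trigger.

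Section 1.2.1.1 gives the interaction factors, expressed as potency-adjusted unbound AUC of abemaciclib plus active metabolites. Clarithromycin, classed as strong, raises it "by 1.7-fold relative to abemaciclib alone in cancer patients". Diltiazem and verapamil, classed as moderate, are predicted to raise it "by 1.7-fold and 1.3-fold, respectively". Itraconazole, classed as strong, has a predicted factor of 2.2.

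**The concern.** The two targets, 100 mg and 50 mg, are also the doses of levels -1 and -2. A level -1 subject who starts clarithromycin or diltiazem, or a level -2 subject who starts itraconazole, is already at the target and receives no reduction for the interaction. A full-dose subject facing the same inhibitor is reduced. The subject who has shown intolerance is not.

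At stake is subject safety: exposure could climb back to about the level that caused the toxicity while the written rule is satisfied. Reduced subjects are foreseeable. Section 1.2.1.2 reports Grade 3 diarrhea in 20% of patients on 200 mg abemaciclib alone and in 13% of those on abemaciclib with fulvestrant, both in breast cancer, and section 3.1.1 requires a step down after Grade 3 diarrhea. How many such subjects would also need one of these inhibitors is not stated.

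**Working it through.** The documents give no figure for exposure in already-reduced subjects, so there is nothing to reproduce. The check applies the protocol's factors to its own dose levels.

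**Inputs.** Dose levels 150, 100 and 50 mg twice daily (section 3.1.1, Table 1). Targets 100 mg and 50 mg (section 7.6). Factors 1.7 (clarithromycin, diltiazem), 1.3 (verapamil) and 2.2 (itraconazole) (section 1.2.1.1). To express exposure as a dose, I rely on the statement in section 1.2.1.1 that, over 50 to 200 mg, "the increase in plasma exposure (AUC) and Cmax was approximately dose proportional".

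**Formula.** Equivalent dose = dose taken under section 7.6 × factor. This is the twice-daily dose that would give the same exposure without an inhibitor. The dose taken is the lower of the current dose and the target, because the rule speaks of reducing.

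| Current dose | Inhibitor | Dose under 7.6 | Equivalent dose | Ratio to current dose | Ratio to dose not tolerated |
|---|---|---|---|---|---|
| 150 mg | clarithromycin, diltiazem | 100 | 100 × 1.7 = 170 | 1.13 | n/a |
| 150 mg | verapamil | 100 | 100 × 1.3 = 130 | 0.87 | n/a |
| 150 mg | itraconazole | 50 | 50 × 2.2 = 110 | 0.73 | n/a |
| 100 mg | clarithromycin, diltiazem | 100 | 100 × 1.7 = 170 | 1.70 | 170/150 = 1.13 |
| 100 mg | verapamil | 100 | 100 × 1.3 = 130 | 1.30 | 130/150 = 0.87 |
| 100 mg | itraconazole | 50 | 50 × 2.2 = 110 | 1.10 | 110/150 = 0.73 |
| 50 mg | clarithromycin, diltiazem | 50 | 50 × 1.7 = 85 | 1.70 | 85/100 = 0.85 |
| 50 mg | verapamil | 50 | 50 × 1.3 = 65 | 1.30 | 65/100 = 0.65 |
| 50 mg | itraconazole | 50 | 50 × 2.2 = 110 | 2.20 | 110/100 = 1.10 |

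Two cases reach or slightly pass the dose not tolerated: 100 mg with clarithromycin or diltiazem, and 50 mg with itraconazole. The other reduced-subject cases stay below it, except that itraconazole at 100 mg does so only because the rule lowers the dose to 50 mg.

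**Sensitivity.** Equivalent exposure passes the dose not tolerated when the factor exceeds 150/100 = 1.5 at level -1, or 100/50 = 2.0 at level -2. A factor 12% lower (1.5/1.7 = 0.88) or 9% lower (2.0/2.2 = 0.91) brings the two level. If each factor may be wrong by 20% either way (my assumption), the ranges are 136 to 204 against 150, and 88 to 132 against 100. The rise over the current dose is less sensitive: with factors 20% lower it is still 1.36-fold (0.8 × 1.7) and 1.76-fold (0.8 × 2.2).

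**After the fix.** A level -1 subject reduced to 50 mg with clarithromycin or diltiazem: 50 × 1.7 = 85, range 68 to 102 on the same assumption. That is below 150 throughout and 15% below the tolerated 100 mg.

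**The case against.** The strongest reply is that section 7.6 already prevents most of this. Clarithromycin and itraconazole are strong inhibitors, to be avoided or substituted, and the fixed doses apply only when that fails. This stands. A reader might infer that the plan takes no preventive step, but the documents do not support that. For these two drugs the gap opens only when use is unavoidable. It does not close the gap for diltiazem, which the instruction on strong inhibitors does not cover.

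Second, a reader might infer that the rule returns subjects to more than the dose they failed. The documents do not establish that. The 13% and 10% excesses are smaller than the plausible error: the diltiazem and itraconazole factors are predictions, the clarithromycin factor comes from a single 50 mg dose, clearance varies with a 51% CV, and dose proportionality is stated for plasma AUC and Cmax while the factors are for potency-adjusted unbound AUC. What stands is the rise of about 1.7-fold or 2.2-fold over the current dose.

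Third, the text can be read as silent on a subject already at the target, since one cannot reduce to the dose one is taking, and the lead-in is permissive. That is fair, but silence leaves the same gap. A literal reading under which a level -2 subject on clarithromycin goes up to 100 mg is not supported, because the rule says to reduce.

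Fourth, other safeguards exist. The Investigator is consulted before any new medication. The Medical Monitor is available for dose decisions (section 11.1). Further reduction is allowed for a toxicity judged to present a risk (section 3.1.1). It would be wrong to infer that subjects go unmonitored: Table 6 makes day 15 labs from cycle 3 conditional on toxicity thresholds, but Table 2 and the hematologic Table 4 in section 3.1.1 also allow ALT and blood counts whenever clinically indicated. These measures limit harm. None states a dose for this situation.

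**Conclusion.** The point holds as a minor safety correction. Section 7.6 has no rule for subjects already reduced for toxicity, and its targets give no reduction in two situations: 100 mg with clarithromycin or diltiazem (about 170 mg-equivalents, roughly the 150 mg not tolerated or slightly above) and 50 mg with unavoidable itraconazole (about 110, against 100 not tolerated). Diltiazem at level -1 is the clearest case, because no avoid-or-substitute instruction applies to it.

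The sizes rest on the protocol's factors being about right in these subjects and on approximate dose proportionality. The number affected is not given; it needs a prior toxicity reduction followed by one of three specific drugs, so it is probably small in a trial of 27 evaluable subjects. Sample size, power and the primary response analysis are not affected.

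**What to change.** Add to section 7.6: (1) a subject already reduced to 100 mg twice daily for toxicity who must take clarithromycin or diltiazem reduces to 50 mg twice daily; (2) the doses in this section never raise a subject's current dose.

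Two cases should be left to the sponsor's clinicians, with the choice written down. One is verapamil at level -1, where staying at 100 mg gives about 130 mg-equivalents and 50 mg gives about 65. The other is unavoidable itraconazole at level -2, where Table 1 has no lower dose and holding abemaciclib is one option. Section 3.1.1 lets such a subject continue nivolumab.

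The cost is a few sentences in an amendment. Level -1 subjects on clarithromycin or diltiazem would have about 15% less exposure than at their tolerated 100 mg. If holding is chosen at level -2, abemaciclib is lost for as long as itraconazole is taken.

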7.7 Laboratory Evaluations

Blood samples will be taken to be tested in the clinical laboratory at intervals specified in **Table 4**

Complete Blood Count:

White blood cell (WBC) count with differential, hemoglobin, hematocrit, and platelet count

Serum Chemistry:

Sodium (Na), potassium (K), chloride (Cl), bicarbonate (HCO₃), calcium (Ca), blood urea nitrogen (BUN), creatinine (Cr), total bilirubin(Tbili), alkaline phosphatase (ALP), AST (SGOT), ALT (SGPT), albumin (Alb)

Coagulation Studies (Screening only):

Prothrombin time (PT) with international normalized ratio (INR), activated thromboplastin time (aPTT)

CONFIDENTIAL

Tumor Markers:

Alpha fetoprotein (AFP). Repeat per **Table 6** schedule only if abnormal at screening.

Thyroid Stimulating Hormone (TSH):

Thyroid stimulating hormone (TSH); if abnormal, check free thyroxine (T4)

Viral Hepatitis Serology and PCR(Screening Only):

Hepatitis B surface antigen (HbSAg), hepatitis B surface antibody (HbSAb), hepatitis B core antibody (HbCAb) total or IgG (IgM only not acceptable), hepatitis C antibody (HCV Ab); if HbSAg or HbCAb positive, check HBV viral load; if HCV Ab positive, check HCV viral load.

Subjects with active hepatitis B and/or hepatitis C are eligible for the study but viral status must be verified using these screening tests. Testing must be sent but results are not required prior to the initiation of study therapy. For subjects known to be positive for hepatitis B or hepatitis C by medical history or prior available laboratory data, viral PCR may be checked concurrently with viral serologies at screening.

For subjects positive for hepatitis B (surface antigen or core antibody positive), HBV viral PCR will be checked on day 1 of every cycle and at the end of treatment visit.

HIV (Screening only):

HIV 1/2 antibody; if positive, check HIV viral load by PCR. Subjects with detectable HIV viral RNA by PCR are not eligible.

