2.3 Exploratory Objective

- To correlate outcomes with blood and tumor tissue immune markers pre- and post-therapy to explore potential biomarkers of anti-tumor response

3 Investigational Plan

Subjects with advanced hepatocellular carcinoma will be enrolled in this single-arm open-label phase II study. Subjects will receive abemaciclib monotherapy 150mg twice daily for seven days then will initiate nivolumab 480mg IV every 28 days while continuing twice daily abemaciclib. Subjects will continue therapy until progression of disease, unacceptable toxicity, or withdrawal of consent.

Figure 1: Treatment Schema

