4.1 Inclusion Criteria

1. Subjects must have hepatocellular carcinoma (HCC) that is inoperable (where surgery is not indicated due to disease extent, co-morbidities, or other technical reasons)
2. Histologic confirmation of HCC is not required for screening but is required prior to initiation of study treatment. Subjects with hepatocholangiocarcinoma or cholangiocarcinoma are not eligible.
3. Tumor must be positive for retinoblastoma (RB) expression by immunohistochemistry
4. Age \geq 18 years and ability to understand and the willingness to sign a written informed consent document.
5. ECOG performance status of 0 or 1
6. Childs-Pugh score of ≤ 7
7. Life expectancy of at least 12 weeks
8. Must be able to swallow tablets
9. Must be willing to comply with protocol procedures (including completion of diaries and outcome measures)
10. Local or loco-regional therapy to the liver (i.e. surgery, radiation therapy, hepatic arterial embolization, chemoembolization, radiofrequency ablation, percutaneous ethanol injection, or cryoablation) must have been completed ≥ 4 weeks prior to enrollment
11. Must be willing to undergo a pretreatment and on-treatment biopsy and have a tumor site that is accessible for core needle biopsy
12. Measurable or evaluable disease as defined by RECIST v. 1.1
13. Women of childbearing potential must have a negative serum pregnancy test performed within 7 days of the first dose of abemaciclib (see Appendix A for definition of childbearing potential). Female subjects of childbearing potential must use an approved contraceptive method (detailed in Appendix A) for the duration of the study and an additional 3 weeks after the final dose of abemaciclib.
14. Subjects with hepatitis B must have an HBV viral load < 100 IU/mL by PCR during screening
15. Must have adequate organ and hematopoietic function as defined below:

Table 5: Baseline Laboratory Parameters

Laboratory Test	Required Value
Absolute neutrophil count (ANC)	$\geq 1.5 \times 10^9/L$
Platelet count	$\geq 75,000 \times 10^9/L$
Hemoglobin	$\geq 8.0 \times 10^9/L$

CONFIDENTIAL

This material is the property of the University of Pennsylvania.

Alanine aminotransferase (ALT)	$\leq 3 \times \text{ULN}$
Aspartate aminotransferase (AST)	$\leq 3 \times \text{ULN}$
Serum creatinine	$\leq 1.5 \times \text{ULN}$
OR creatinine clearance (CrCl)	OR $\text{CrCl} \geq 50 \text{mL/min}$ by Cockcroft-Gault Formula
Total bilirubin	$\leq 2.0 \times \text{ULN}$
Serum albumin	$\geq 2.8 \text{ g/dL}$

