6.1 Screening (Within 28 days of First Dose)

- Signed written and informed consent
- Review and confirm all inclusion/exclusion criteria
- Complete medical history and demographics
- Complete physical examination including but not limited to: height, weight, vital signs (oxygen saturation, heart rate, respiration rate, blood pressure, and oral temperature)
- ECOG performance status
- Concomitant medications
- Clinical laboratory testing including but not limited to:
 - CBC with differential and platelet count
 - Serum chemistries: sodium (Na), potassium (K), chloride (Cl), bicarbonate (HCO₃), blood urea nitrogen (BUN), creatinine (Cr), calcium (Ca), albumin (Alb), total serum bilirubin (TBili), AST (SGOT), ALT (SGPT), alkaline phosphatase (ALP)
 - Prothrombin time (PT)/International normalized ratio (INR)
 - Activated thromboplastin time (aPTT)
 - Thyroid stimulating hormone (TSH)
 - If abnormal, free thyroxine will be performed
- Alpha fetoprotein (AFP)
- HIV serology
 - HIV 1/2 antibody screen; HIV viral load by PCR if antibody screen positive
- Serum pregnancy test for beta HCG (for women of childbearing potential, defined in Appendix A)
- Serologic testing for hepatitis C and hepatitis B:
 - Hepatitis B screening with hepatitis B surface antigen, surface antibody, and core antibody (IgG or total antibody, not IgM); if hepatitis B surface antigen or core antibody is positive, HBV DNA PCR will be performed
 - Hepatitis C screening with HCV antibody; if positive, HCV RNA PCR will be performed. HCV RNA PCR can also be performed on cycle 1 day 1, and results are not required prior to initiating therapy.
 - For subjects known to be positive for hepatitis B or hepatitis C by medical history, viral PCR should be performed concurrently to antibody studies
- Blood draw (50cc) for correlative research studies (procedures described in laboratory manual)
- Per standard of care, baseline imaging including but not limited to chest CT (with or without contrast) and triphasic abdominopelvic CT or MRI, if subject does not have previous documentation within 3 weeks of first dose
- Core or surgical tumor biopsy (procedures described in laboratory manual)

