6.2.1.1 Day 1 - Baseline Visit

- Focused physical exam
- Vital signs and weight
- ECOG PS
- CBC with differential and platelet count and serum chemistries (Na, K, Cl, HCO₃, BUN, Cr, Ca, Alb, TBili, AST, ALT, ALP)
- AFP (only if elevated at screening)
- Serum pregnancy test for beta HCG (for women of childbearing potential, defined in Appendix A)
- Review of concomitant medications
- HCV and HBV viral PCR if indicated:
 - HBV DNA PCR only if hepatitis B surface antigen or core antibody positive
 - HCV RNA PCR if hepatitis C antibody positive and not performed at screening
- Dispensing of abemaciclib

CONFIDENTIAL

- Baseline AE assessment

6.2.1.2 Day 8

- Focused physical exam
- Vital signs and weight
- ECOG PS
- CBC with differential and platelet count and serum chemistries (Na, K, Cl, HCO₃, BUN, Cr, Ca, Alb, TBili, AST, ALT, ALP)
- Blood draw (50cc) for correlative research studies (procedures described in laboratory manual)
- AE assessment
- Nivolumab treatment

6.2.1.3 Day 15 (biopsy and lab visit when possible on same day between days 15 and 19)

- CBC with differential and platelet count and serum chemistries (Na, K, Cl, HCO₃, BUN, Cr, Ca, Alb, TBili, AST, ALT, ALP)
- Core or surgical tumor biopsy (procedures described in laboratory manual)
- Blood draw (50cc) for correlative research studies (procedures described in laboratory manual)

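### Section 7.7 lets study therapy start before hepatitis B results are back, although inclusion criterion 14 sets an HBV DNA limit for entry

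*Combined protocol and SAP*

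**What the plan says.** Four places in the combined protocol and SAP bear on when viral hepatitis results must be known.

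- **Section 4.1, inclusion criterion 14:** "Subjects with hepatitis B must have an HBV viral load < 100 IU/mL by PCR during screening".
- **Section 6.1, Screening:** the site is to "Review and confirm all inclusion/exclusion criteria". The hepatitis B bullet calls for HBV DNA PCR when surface antigen or core antibody is positive and says nothing about proceeding without the result. The hepatitis C bullet adds: "HCV RNA PCR can also be performed on cycle 1 day 1, and results are not required prior to initiating therapy".
- **Section 6.2.1.1, cycle 1 day 1:** the HBV line reads "HBV DNA PCR only if hepatitis B surface antigen or core antibody positive". Only the HCV line is worded to allow a test that was not done at screening.
- **Section 7.7, Laboratory Evaluations:** "Subjects with active hepatitis B and/or hepatitis C are eligible for the study but viral status must be verified using these screening tests". The next sentence is "Testing must be sent but results are not required prior to the initiation of study therapy".

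**The concern.** A numerical entry limit cannot be confirmed until the number is known. Section 7.7 nevertheless allows treatment to begin without it, for both viruses. A site following 7.7 as written could start a subject with hepatitis B whose HBV DNA later proves to be 100 IU/mL or more, so that one section authorises what another forbids.

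This is a matter of patient safety and eligibility. Criterion 14 is the only place where an HBV DNA value has a stated consequence. The dose-modification rules in sections 3.1.1 and 3.2 respond to transaminases and bilirubin and do not mention HBV DNA. The schedule repeats HBV DNA on day 1 of each cycle, but no action is attached to the value. The protocol also does not say what to do with a subject already dosed whose screening result comes back too high.

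**Working it through.** The plan states no figure to reproduce. The check is a comparison of texts, followed by one line of schedule arithmetic.

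**Step 1: what each section requires before the first dose.**

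| Section | HBV DNA | HCV RNA |
|---|---|---|
| 4.1, criterion 14 | Below 100 IU/mL, during screening | No limit in this criterion |
| 6.1 | Tested if a marker is positive; all criteria confirmed; no waiver | Result expressly not needed before dosing |
| 6.2.1.1 | Tested on day 1 if a marker is positive; no wording that defers the screening test | May be done on day 1 if not done at screening |
| Table 6, hepatitis footnote | Tested at screening, then day 1 of each cycle; no waiver | Tested if antibody positive; no waiver |
| 7.7 | Result not needed before dosing | Result not needed before dosing |

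The HCV column is consistent: no HCV RNA limit is set, so starting without the result breaks no criterion. In the HBV column, 7.7 is the only entry that dispenses with the result.

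**Step 2: can the 7.7 sentence be read as applying to HCV alone?** It directly follows a sentence naming both viruses, and the block it belongs to lists both the HBV and the HCV viral load. Nothing elsewhere narrows it, and no rule of precedence between sections is given.

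**Step 3: could criterion 14 refer only to the date of the sample?** Its phrase about screening might be read that way. But 6.1 requires the criteria to be confirmed at screening, and a pending result confirms nothing.

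**Step 4: possible exposure.** Section 3 states: "Subjects will receive abemaciclib monotherapy 150mg twice daily for seven days then will initiate nivolumab 480mg IV every 28 days". Section 7.7 sets no latest date for the result.

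- Result after cycle 1 day 1: abemaciclib has already started.
- Result after cycle 1 day 8: 7 days × 2 doses per day = 14 scheduled abemaciclib doses, plus nivolumab 480 mg.

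**Step 5: conditions for harm.** Three things must coincide: the subject is positive for surface antigen or core antibody, the site doses before the result is known, and the result is 100 IU/mL or more. The documents give no HBV prevalence, no laboratory turnaround time and no risk of reactivation, so no expected number can be calculated.

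**The case against.** The best defence is that 7.7 permits early dosing without instructing it. Criterion 14 is mandatory, 6.1 requires confirmation, and 7.7 itself says viral status must be verified by the screening tests. On this view no two rules are impossible to follow together, and one sentence is merely scoped too loosely. It is true that a careful site can satisfy everything. But verification with no date attached, followed at once by permission to start without results, still allows an ineligible subject to be dosed.

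Three further points have some force.

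- Section 6.1 does not say outright that HBV results must precede dosing. It confines its waiver to HCV by placement, so its disagreement with 7.7 is one of scope. The direct conflict is with criterion 14.
- Section 7.7 repeats an HIV limit ("Subjects with detectable HIV viral RNA by PCR are not eligible") but omits the HBV one. This contrast is weak evidence, since 7.7 also leaves out the other laboratory entry limits in section 4.1.
- Early dosing would not go unmonitored. Chemistries are due on cycle 1 days 1, 8, 15 and 29. Nivolumab is withheld or stopped on transaminase or bilirubin thresholds. The hepatic work-up table includes hepatitis B serology. Antivirals are permitted, and the investigator may withdraw a subject for safety. These measures respond to liver injury or to clinical judgement; none replaces a check of HBV DNA before the first dose.

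Finally, the lack of an action rule for on-treatment HBV DNA is a separate gap that the proposed edits do not close. It matters here only because it leaves the entry check as the sole written safeguard tied to that value.

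**Conclusion.** The concern holds. Section 7.7 as written permits dosing before a safety entry criterion has been confirmed, contrary to criterion 14 and more broadly than 6.1 or 6.2.1.1 allows. That active hepatitis B is eligible in principle is compatible with criterion 14 and is not part of the conflict.

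The size is unknown and may be zero subjects. The exposure of 14 scheduled abemaciclib doses plus one nivolumab infusion assumes a result still outstanding after day 8, with the planned schedule followed; nothing in the documents shows that such a delay is likely. Confidence is high on the textual conflict. The clinical consequence cannot be quantified from the documents. The text should be corrected, since the protocol should not authorise a breach of its own entry limit.

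**What to change.** Make three wording changes in section 7.7.

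1. Replace the general waiver with: *HCV RNA results are not required prior to the initiation of study therapy.* This matches 6.1.
2. Add: *For subjects positive for hepatitis B surface antigen or core antibody, the HBV DNA result must be available and < 100 IU/mL before cycle 1 day 1 dosing.* Hepatitis B serology must therefore also be back by then, because it triggers the PCR.
3. Add *subject to inclusion criterion 14* to the sentence on eligibility of active hepatitis B, as a clarification.

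No test is added. Serology and PCR are already in the screening panel, and 6.1 already asks for PCR alongside serology in subjects known to be positive. The cost is a short wait for the result in HBV-positive subjects, within the 28-day screening window.
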